Conducting a beta test to confirm the protocol, including the software functionality and surveys. Before rolling out the RCT, we may conduct a beta test to pilot the recruitment, enrollment, data collection, and randomization procedures, as well as to identify final opportunities to improve the content. In most cases, five is a sufficient number of testers to identify any issues. Here, we propose 15-20 youth so that ~10 youth will test the functionality of the intervention program and ~5 the functionality of the control program. Usability data will be collected weekly via text messaging from participants. We may send questions weekly via text messaging, or by phone for non-responders, about the program experience. At the end of the beta test, we may conduct one-on-one interviews to identify any additional experiential issues that need to be addressed before the RCT is launched.

Pilot RCT of BullyDown (n = 150)

Randomization and group assignment. Once youth complete the baseline survey, they will be randomly assigned to either the intervention (n = 76) or the control (n = 74) group. We will use a computerized minimization technique, as originally described by Taves⁵⁹ and more recently reviewed by others,⁶⁰⁻⁶² to balance the sample on youth key indicators. These may include sex, school or Club, and bullying perpetration history. Treatment assignment will be generated and maintained at a password-protected Internet website monitored by [name].

Contamination. Studies across participant populations and behavioral targets report that contamination is uncommon and does not affect study outcomes.^{63,64,65,66} Give this, and to be efficient with R21 resources, students will be randomized at the individual rather than school or Club level. As we have done previously,^{63,64} we will ask questions at intervention end that are specific to the BullyDown content. If indicated, we will include the number of correct exposure

questions as a proxy for contamination in multivariate models.

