Data collection. Measures will be collected online at baseline, intervention end, and 3 months post-intervention end. All participants, regardless of study condition, will complete assessments at each time point. Youth will be able to complete the surveys on their own (e.g., at home). If they are attending the brick and mortar school or Club, they also will be able to complete the survey at school or Club in the computer lab if they would prefer. To facilitate self-completion, youth will receive an invitation text message with a unique URL to access the survey. This allows participants to complete the survey at a time and place convenient for them. Alternatively, they can sign up for one of the survey sessions at school or Club that the research staff will schedule with the school or Club administration. To avoid unintentional influence that school and Club staff may have on youth survey answers, only research staff will be present in the computer lab during survey administration.

3D. MEASUREMENTS AND STUDY INSTRUMENTS

Most of the proposed measures below were used in the beta test, suggesting the survey length can be feasibly completed by adolescents in middle school or between the ages of 12-14 year of age. Measures are as follows:

Table 3. BullyDown assessment measures		
Main Outcome measures (intervention end)	Acceptability	We will measure intervention acceptability and tolerability ⁶⁷ with a combination of open-ended questions (e.g., “What aspect of the program did you like the least?”) and questions that form a scale of intervention acceptability (e.g., I liked my Text Buddy; $\alpha = .87$). Participants will estimate the number of messages they received in the past week and percent that they read. The program will record the number of weekly level-up questions answered, and the number answered correctly, as well as the number of Text Buddy and Forever Friend messages sent.
	Feasibility	We will monitor the number of eligible/ineligible youth, the number of parental permission forms received, the number of youth invited but who decline to take part, and the retention rate.

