Baseline covariates will be examined to determine whether randomization performed as intended. Any that are significantly imbalanced across study arms will be included in multivariate analyses.

We will use logistic regression to analyze outcomes (e.g., bullying perpetration, other aggressive behaviors; bystander behavior). Once gross estimates of intervention effect have been calculated, covariates will be added to examine

whether they appear to mediate the relation between group assignment and the outcome. Three conditions must be met in order to claim that mediation is present:⁹³⁻⁹⁵ (1) a predictor (e.g., experimental arm) is significantly associated with a mediator (e.g., TPP motivation); (2) The mediator is significantly associated with an outcome (e.g., pregnancy); and (3) when one controls for the mediator, the effect of the predictor on the outcome becomes non-significant. If this effect retains significant but is attenuated, partial mediation is indicated. A 10% or greater change in the point estimate will be deemed clinically significant.^{96,97}

Sex as a biological variable. It is possible that males will respond to the program differently than females because it feels more individual and perhaps, in this way, will resonate more with males.⁸³ Conversely, perhaps because females text message at a greater volume than males,^{36,84} the format of this program may resonate more with them. As such, sex will be explicitly examined as a potential moderator. To understand whether the intervention impact varies by sex, we will test an interaction term, i.e., experimental group X sex. If the term is statistically significant, then it will suggest that boys and girls are impacted differentially by the intervention.

To examine whether/how the intervention effect attenuates over time, we will use generalized estimation equations to analyze the data across follow-up periods using an identity link and exchangeable correlation structure. By entering an interaction term for experimental group X time, we can determine if the intervention is differently impactful at intervention end versus 3-months post-intervention.

Should [name] need statistical guidance, we will take advantage of [name] access to the biostatistics 'core' at the University of North Carolina (please see Budget Justification).

Power analysis

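### The mediation steps omit the baseline mediator and baseline outcome, and adjusting only for between-arm imbalance leaves mediator-outcome confounding within arms

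*Combined protocol and SAP*

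**What the plan says.** Section 3E (Specific Aim 2) first estimates the arm effect on each behavioral outcome: "We will use logistic regression to analyze outcomes". It then adds unnamed covariates to see "whether they appear to mediate the relation between group assignment and the outcome". Three conditions must all hold before mediation is claimed:

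1. "a predictor (e.g., experimental arm) is significantly associated with a mediator".
2. "The mediator is significantly associated with an outcome (e.g., pregnancy".
3. The arm effect loses significance once the mediator is controlled. Attenuation that stays significant is read as partial mediation, and a change of 10% or more in the point estimate is treated as clinically significant.

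No step includes the baseline value of the mediator or of the outcome. The one rule for baseline covariates in that section is "Any that are significantly imbalanced across study arms will be included in multivariate analyses".

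The baseline data should be available. Section 3C (Data collection) says "Measures will be collected online at baseline, intervention end, and 3 months post-intervention end". Section 3C (Randomization and group assignment) says of the balancing factors "These may include sex, school or Club, and bullying perpetration history".

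No mediator or measurement wave is given for this trial. The illustrative mediator and outcome (TPP motivation, pregnancy) come from another topic. Section 3D lists the SEL components as exogenous variables, not as mediators. Only a score taken after randomisation can respond to arm, and SEL is the program's guiding model (section 2), so post-randomisation SEL scores are the likely mediators. That is inference.

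**The concern.** Randomisation protects condition 1 from bias. It does not protect condition 2, which compares youth who differ in mediator level, and that level is not randomised. A young person low in empathy at baseline may stay low and may also bully more, whether or not BullyDown changed anything. Such a trait can be perfectly balanced between arms and still create a mediator-outcome association within each arm, so a rule triggered by between-arm imbalance does not address it. If bullying history is used as a minimization factor, it is even less likely to be imbalanced and so to enter under the rule.

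Two consequences follow. Condition 2 can be met by an SEL component that has no effect on bullying, which weakens one of the three safeguards. And condition 1 is tested with more residual variance than necessary, so a component that the program does change is easier to miss.

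**Working it through.** The plan gives no power calculation and no correlations, so there is no stated figure to reproduce.

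**Inputs from the documents.** Allocation 76/74 (section 3C). Retention criterion 80% at 3 months (section 3E), giving 0.8 × 76 ≈ 61 and 0.8 × 74 ≈ 59, or 120 completers. Bullying prevalence 20–24% (section 1), midpoint 22%, giving 0.22 × 120 ≈ 26 events.

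**Assumptions, not in the documents.** Two-sided alpha 0.05; arm effect on the mediator d = 0.4 SD; baseline-to-follow-up correlation r of the SEL score 0.3 to 0.7; correlation rho (absolute value) between the stable SEL trait and stable bullying propensity; correlation of latent bullying propensity over time 0.5.

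**Condition 1 (arm to mediator).** Adjusting for the baseline score multiplies the residual SD by √(1 − r²). By the normal approximation, power = Φ(d / [√(1 − r²) × √(1/61 + 1/59)] − 1.96), with √(1/61 + 1/59) = 0.1826.

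- Unadjusted: 0.4/0.1826 = 2.191; Φ(0.231) = 59.1%.
- r = 0.3: 2.191/0.954 = 2.296; Φ(0.336) = 63.2%.
- r = 0.5: 2.191/0.866 = 2.530; Φ(0.570) = 71.5%.
- r = 0.7: 2.191/0.714 = 3.068; Φ(1.108) = 86.6%.

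A t-test calculation at 60 per arm gives about 58% unadjusted and 62%, 71% and 86% adjusted. The gain is about 4 points at r = 0.3 and 28 at r = 0.7.

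**Condition 2 (mediator to outcome).** Logistic simulation with 61/59 completers, 22% bullying, a 0.4 SD arm effect on the mediator, no arm effect on bullying and no mediator effect on bullying. A stable trait drives the SEL score at both waves and is correlated with a stable bullying propensity. Percentage of 1,500 trials per setting with p < 0.05 for the mediator:

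| r | rho | Mediator alone | + arm, baseline SEL | + arm, baseline SEL, baseline bullying |
|---|---|---|---|---|
| 0.5 | 0 | 4 | 5 | 5 |
| 0.5 | 0.3 | 20 | 10 | 8 |
| 0.5 | 0.5 | 47 | 20 | 13 |
| 0.5 | 0.7 | 76 | 34 | 24 |
| 0.7 | 0 | 5 | 5 | 5 |
| 0.7 | 0.3 | 25 | 8 | 7 |
| 0.7 | 0.5 | 61 | 17 | 11 |
| 0.7 | 0.7 | 90 | 28 | 21 |

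A separate simulation over correlations 0.2 to 0.5 gave about 10–62% unadjusted and 4–14% adjusted.

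**Conditions 1 and 2 together.** With no arm effect on the mediator, condition 1 passes about 5% of the time. If the two tests are roughly independent, the joint rate is about 0.05 × (10% to 62%) = 0.5% to 3.1%; simulated, 0.5% to 3.5%. With a 0.4 SD effect the product is about 0.58 × (10% to 62%) = 6% to 36%; simulated, 6% to 33%.

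**The case against.** The strongest reply is that condition 2 never stands alone. A reader might take the 10–60% as the chance of a false mediation claim; the plan does not support that, because all three conditions must hold. If the program does not move a component, condition 1 screens it out. If condition 3 is read as requiring an initially significant arm effect on bullying, a further simulation (baseline correlations 0.2–0.4, a 0.4 SD arm effect on the mediator, no arm effect on bullying) gave a full-mediation claim in at most 1.3% of trials, and 2–9% when a real direct arm effect on bullying was added. This stands and limits the concern to components that the program truly changes. Under a looser reading of condition 3 the rate stays nearer the joint rate for conditions 1 and 2.

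Three other stronger readings also fail:

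- A reader might infer that the plan commits to an unadjusted follow-up SEL score. It names neither mediator nor wave, and an imbalanced baseline score would be added. The defect is the absence of pre-specified baseline terms, together with that conditional rule.
- A reader might expect adjustment to restore the 5% error rate. It does so only if the measured baselines carry all the confounding. With stable latent traits, 7–24% remains in the table above for nonzero rho. Section 3D reports alphas of .62 for empathy, impulsivity and willingness to intervene and .68 for support for cultural pluralism, so some baseline scores are imperfect proxies.
- A reader might infer that mediation results will select R01 content. Section 3E says that the behavioral analyses mainly inform R01 power, and no section gives mediation that role.

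It is also fair to say that condition 1 is valid as written, and that the plan declines any power analysis for this pilot. The precision argument is about efficiency only.

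**Conclusion.** The point holds as a cheap improvement to an exploratory analysis, of minor to moderate weight; the main outcomes are feasibility and acceptability. The omission is plain in section 3E, the imbalance rule does not cure it, and the data needed are already collected.

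The size rests on assumed correlations. For trait correlations of 0.2 to 0.5, condition 2 is met in roughly 10% to 60% or more of trials with no mediator effect, against about 4% to 14% after adjustment and up to about 24% under stronger correlations. With no trait correlation there is no inflation. The practical exposure is the case in which the program moves the component without that component affecting bullying: conditions 1 and 2 then both hold in about 6% to 33% of trials. For condition 1, the cost is lost power, about 58% instead of 62% to 86% for a 0.4 SD effect.

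**What to change.** Revise the mediation paragraph of section 3E as follows.

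1. Name the mediators and the wave at which each is taken, and replace the examples from the other topic.
2. Fit condition 1 as the post-randomisation mediator on arm plus the baseline value of that mediator.
3. Fit condition 2 and the mediator-adjusted arm model with arm, the baseline mediator and the baseline version of the outcome as covariates, whatever the balance tests show.
4. Compare the arm effect with and without the mediator using the same baseline covariates in both models. Otherwise the 10% change criterion mixes the effect of adding the mediator with that of adding the covariates.
5. State that mediator-outcome confounding may remain after adjustment, because several baseline scales have modest reliability.

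The cost is wording only, with no new data. The downside is two or so extra terms in logistic models with about 26 expected bullying events, so intervals for the mediator-outcome association will be wider.

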Specific Aim 2: Pilot test the 7-week BullyDown primary prevention program for feasibility and acceptability in an RCT of 150 middle adolescents. Youth will be randomly assigned to either BullyDown, a 4-message-per-day program, or an attention-matched control group talking about ‘healthy lifestyle’ topics (e.g., exercise). Our main outcome measures will be feasibility (e.g., recruitment and enrollment rates) and acceptability (e.g., positive program appraisal) at intervention end. The behavioral outcomes we will measure to motivate power analyses for a future R01 include: (1) bullying perpetration, (2) other aggressive behavior directed towards peers, and (3) bystander behavior in the past 30 days at 3-month post-intervention. We also will examine behavioral indicators at intervention end to observe proximal effects.

Given the limited impact of existing school-based interventions and the time associated with implementing them during school time, more efficient and effective intervention methods are needed. Programs that can be delivered to youth in middle adolescence, typically of middle school aged, irrespective of whether they are attending school physically or virtually may be especially relevant as school boundaries become more fluid. BullyDown addresses this critical need by providing a scalable program that could be quickly and cost-effectively disseminated nationally. If efficacious, we will test the intervention in an R01-funded RCT. Future endeavors could include adapting the program for Spanish-speaking youth and dynamically tailoring content to reported bullying behaviors.

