Changed phone numbers. We have found stability of cell phone numbers to be high in [name]'s other text messaging-based programs. We expect the same will be true for BullyDown. In fact, none of the participants in the beta test dropped out because of non-working or changed phone numbers. If participants are non-responsive to program prompts, we will reach out to them via text, email, and telephone. If that is unsuccessful, a member of the research team will visit the school or Club to check on the participant. During the enrollment phase, we will explain to participants the importance of recording the project phone number somewhere convenient for them so they can contact us if they change their cell phone number.

Assertive follow-up. For each data collection period, we will send automated reminders to youth who have not completed the survey via text messaging. We will engage in personalized outreach if the survey is not completed within a week of the initial invitation. If youth are attending brick and mortar school or BCGA Club, we also will schedule in-school and in-Club data collection so that youth have multiple opportunities to complete the survey, especially if they were absent on a particular day. To maximize data, we also will include youth in the 3-month post-intervention survey even if they have missed the intervention end survey.

Specific Aim 1: Finalize BullyDown content.

Updating content to reflect current school interactions and realities (n=60). Current messages focus primarily on in-person scenarios. We will build upon the development work described above by updating the content so that it better reflects online as well as offline peer interactions. To do so, we will conduct FGs to obtain youth voice about their current experiences with peers online. While it is unlikely that schools will remain online indefinitely, technology is continually being infused into classroom exercises and so we anticipate online interactions to persist even in post-Covid-19 school curriculum.

FGs will be stratified to promote a sense of shared experiences. Stratification characteristics may be sex, race/ethnicity, among others. To promote a diversity of experiences, we will purposefully recruit youth with a variety of bullying experiences. More information can be found in Recruitment and Retention.

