Transcripts of the FGs will be entered into Dedoose (formerly EthnoNotes),⁸⁵ a mixed methods analysis program. Codes will be generated based on the first FG, reexamined, and refined through constant comparison with the second FG.⁸⁶ A codebook will be created with codes, brief descriptions, and illustrative quotations.⁸⁷ Codes will be both generated inductively and derived from our initial research questions (e.g., how youth interact with their peers and their teacher online). [name] project coordinator and [name] graduate research assistant will code both FGs. To assure inter-coder reliability, we will calculate a kappa value and accept a minimum of 0.75 as the criterion for adequate agreement between coders.⁸⁸ After coding is complete, we will extract themes using an iterative process to highlight evidence contradictory to our conclusions as well as the modal response.⁸⁹ The analysis will result in a report that describes the findings and advises how to integrate them into program content.

Specific Aim 2: Pilot test the 7-week BullyDown intervention for feasibility and acceptability in an RCT of 150 adolescents either in middle school and/or 12-14 years of age.

The **feasibility** of the BullyDown intervention will be determined by our recruitment and retention rates. If at least 75% of eligible studies assent and 80% complete the survey at 3-months post-intervention, we will deem these data points as supportive of a hypothesis of feasibility.

The **acceptability** of program features (e.g., badges, Text Buddy) will be measured using 5-point Likert scales; average scores of 4 or more will be supportive of acceptability.⁹⁰ Youth engagement with the program will be examined to identify potential trends in greater intervention impact (e.g., for those who use the Text Buddy feature).

Post-intervention one-on-one interviews to illuminate the intervention experience will be analyzed using a thematic approach,⁹¹ as our aim will be more descriptive in nature, with a lower level of interpretation needed than is afforded by grounded theory or other qualitative analytical techniques.⁹²

Analyses examining **behavioral outcomes** will be primarily intended to inform power analyses for the larger R01. Data will be treated as intention-to-treat and complete case. We will conduct sensitivity analyses (e.g., missing = bullying behavior) to understand how this may affect our findings. Missing data that are not the main outcomes will be imputed.

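### Mediation is judged by whether the arm effect loses significance after adjustment; no indirect effect with an interval is planned, and the need for a significant total effect is only implied

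*Combined protocol and SAP*

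**What the plan says.** Section 3E, under Specific Aim 2, first estimates the gross intervention effect by logistic regression; then "covariates will be added to examine" whether they appear to mediate it. "Three conditions must be met in order to claim that mediation is present": arm is significantly associated with the mediator, the mediator is significantly associated with the outcome, and "when one controls for the mediator, the effect of the predictor on the outcome becomes non-significant". A further sentence adds: "If this effect retains significant but is attenuated, partial mediation is indicated". The paragraph names no indirect effect, no interval for one, no mediator from this trial and no wave for the mediator.

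Other sections fill part of that gap. Section 3D lists the social-emotional learning (SEL) components as a numbered class of their own. Section 2, Specific Aim 2, sets the behavioural outcomes at three months after the intervention, and adds: "We also will examine behavioral indicators at intervention end to observe proximal effects".

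On missing data, Section 3C states that "we also will include youth in the 3-month post-intervention survey even if they have missed the intervention end survey", and Section 3E that "Missing data that are not the main outcomes will be imputed".

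**The concern.** A mediation claim, and the split between full and partial, depends on which side of a significance threshold the adjusted arm effect falls. That is not a measure of how much of the effect passes through the mediator. A non-significant adjusted effect in a trial of 150 may only reflect low power.

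The verbs *becomes* and *retains* presuppose a total effect that was significant to begin with, yet the numbered list does not ask for one. Two analysts could follow the paragraph on the same data and differ on whether mediation is claimed.

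Section 2 says that the SEL model guides the programme, and Section 3E says that the behavioural analyses mainly inform power analyses for the larger trial. An indirect effect with its uncertainty would be useful there. A changed significance label would not.

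**Working it through.** The plan states no alpha, effect size, power or mediation figure, so there is nothing to reproduce. The check is a simulation of the rule.

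**Inputs from the documents**
- Allocation 76/74 (Section 3C).
- The 80% retention threshold (Section 3E) gives 0.8 × 150 = 120. By arm, 0.8 × 76 = 60.8 and 0.8 × 74 = 59.2, so 61/59.
- Control rate (20 + 24)/2 = 22% (Section 1). That figure is per semester, whereas the trial outcome in Section 3D is three or more times in 30 days. Using it here is an assumption.

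**Assumed:** two-sided alpha 0.05 and all path sizes.

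**Model.** Mediator M = a·arm + e, with e standard normal; logit P(Y = 1) = b0 + c'·arm + b·M. Full mediation means c' = 0. On the logit scale the indirect path a × b runs from 0.5 × (-0.8) = -0.40 to 0.8 × (-1.0) = -0.80.

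**Rules compared**
- Strict: conditions 1 to 3, or the partial-mediation sentence, plus a significant total effect. Its claim rate cannot exceed the power for the total effect.
- Lenient: conditions 1 to 3 as numbered.
- Joint: conditions 1 and 2 only.

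**Full mediation, 4,000 trials per setting (%)**

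| Arms | a, b | Total effect significant | Strict | Condition 3 met | Lenient | Joint |
|---|---|---|---|---|---|---|
| 61/59 | 0.5, -0.8 | 11.7 | 9.2 | 95.6 | 65.5 | 68.3 |
| 61/59 | 0.6, -1.0 | 18.6 | 17.0 | 95.5 | 82.2 | 86.0 |
| 61/59 | 0.8, -1.0 | 28.2 | 27.0 | 96.2 | 91.2 | 94.7 |
| 76/74 | 0.5, -0.8 | 13.8 | 12.3 | 95.6 | 78.4 | 82.0 |
| 76/74 | 0.6, -1.0 | 22.2 | 21.4 | 95.2 | 89.7 | 94.1 |
| 76/74 | 0.8, -1.0 | 32.1 | 31.6 | 95.7 | 94.0 | 98.2 |

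Repeat runs put the strict rate at 8 to 33%. The strict column sits just under the total-effect column: the total effect is the bottleneck. The lenient column is close to the joint column times the condition 3 rate; in the first row, 0.683 × 0.956 = 0.653, against 65.5% simulated. When the direct effect is nil, condition 3 is a test of a true null and passes about 95% of the time.

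**Large direct effect (assumed odds ratio 0.4).** Condition 3 is met in about 61 to 79% of trials, and strict-or-partial claims occur in about 37 to 78%. At a = 0.8, b = -1.0, the share meeting all three conditions fell from 73% at 61/59 to 69% at 76/74: more data made the third condition harder to satisfy.

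**Smaller shift (a = 0.2 to 0.3, full mediation).** Strict 2 to 7%, joint 17 to 43%. Every method misses most mediation.

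**Proposed procedure.** Bootstrap interval for the indirect effect on the risk-difference scale, adjusted for baseline, with 20% of mediators missing (assumed) and imputed within each resample; 800 trials per setting:

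| Arms | Detected, a = 0.3, b = -1.0 | Detected, a = 0.5, b = -0.8 | Detected, a = 0.8, b = -1.0 | Median interval width (points) |
|---|---|---|---|---|
| 61/59 | 27.3% | 47.2% | 74.6% | 13.2 to 19.8 |
| 76/74 | 41.5% | 63.7% | 87.5% | 11.6 to 18.1 |

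With one path null, false claims are 2.6 to 3.0% with missing mediators and 3.5 to 6.0% without.

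**Confounding.** Assume no true mediator effect and a confounder (correlation 0.3 to 0.7 with the mediator, log odds ratio -1.0 per SD on the outcome). The baseline-adjusted bootstrap then makes false claims in 10 to 23% of trials if the confounder is stable from baseline and in 22 to 79% if it arises later. The strict rule stays at 0.1 to 2.3%, because it rarely claims anything.

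**The case against.** **The wording favours one reading.** An effect cannot become non-significant unless it was significant, and gross effects are estimated first. This is fair: the strict reading is the more natural one. The requirement is still absent from the numbered list, and the strict reading is the one that loses most true cases under full mediation.

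**The contrast depends on full mediation.** A reader might infer that condition 3 always either adds nothing or blocks most claims. The documents give no path sizes that would support this, and with a direct odds ratio of 0.4 neither half holds.

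**The gain is modest.** Against the lenient reading, the joint test adds only about 1 to 5 points in the table. The proposed procedure's 47 to 88% is also not a like-for-like comparison with the strict 8 to 33%: it uses baseline adjustment and has mediators missing, and no rate for the current rule under those conditions is available. What is gained is an estimate with its uncertainty and one unambiguous analysis, not assured power. Under confounding, the proposal can produce more false claims than the strict rule. All of this stands.

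**The plan is less open than it looks.** Section 2 makes three months the behavioural time point, and Section 3D separates the SEL scales from demographics and literacy. It would be wrong to say that the outcome wave is left open. What is missing is a link from those choices to the mediation paragraph.

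**Two details invite more weight than they bear.** "A 10% or greater change in the point estimate will be deemed clinically significant" might be read as another route to a mediation claim, but nothing in the paragraph makes it one. The examples in the rule come from another topic, but they are only illustrations and change no analysis.

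**Conclusion.** The point holds and is minor. The rule rests on a change of significance label, plans no indirect effect with an interval, and leaves the total-effect requirement unstated. Under full mediation with the assumed paths, the strict reading claims mediation in about 8 to 33% of trials where a joint test would in about 68 to 98%; the lenient reading makes condition 3 nearly redundant. With a large direct effect the contrast shrinks.

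All of these sizes rest on assumed paths, an assumed alpha and a control rate borrowed from a different recall period.

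A reader might infer that the trial's conclusions are at risk. They are not: Specific Aim 2 is about feasibility and acceptability, mediation is in neither aim, the wording is exploratory, and no decision rule uses it.

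**What to change.** Replace condition 3 and the partial-mediation sentence with an estimated indirect effect and its 95% bootstrap or Monte Carlo interval, for example on the risk-difference scale, and state that a significant total effect is not required.

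- Name the Section 3D SEL scales at intervention end as mediators and three-month behaviour as the outcome. Behaviour items cover the past 30 days and the programme lasts 7 weeks (49 days), so behaviour reported at intervention end falls within the programme, before the mediator is measured.
- Adjust for baseline mediator and baseline outcome.
- Impute missing mediators within each resample, since youth who miss the intervention-end survey are kept.
- State the assumption of no unmeasured mediator-outcome confounding, and report the results as exploratory.

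The cost is analysis work only; no new data are needed. The downsides should be stated with the results: intervals about 12 to 20 percentage points wide, detection of about 27 to 42% at a 0.3 SD shift with 20% of mediators missing, and confounding that is not cured.
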